11.5.2.1 Pregnancy

If the female partner of a treated male subject becomes pregnant, the male subject must notify the Investigator within 24 hours of learning of the pregnancy. The Investigator must make every effort to ensure that the pregnant female is aware of the need to notify her healthcare provider regarding her male partner's participation in this clinical trial and his potential exposure to casimersen, eteplirsen or golodirsen.

The study site must complete a pregnancy form within 24 hours of learning of the pregnancy and send to the DSMB. The study site will make every effort to follow the pregnancy until outcome is known.

11.5.2.2 Overdose

An overdose is defined as administration of a dose that is >10% higher than the assigned dose per the protocol. An overdose will be reported even if it does not result in an AE. An overdose will be recorded on the appropriate form and sent to the DSMB or designee within 24 hours.

Medication Error

Medication Error is any preventable incident that may cause or lead to inappropriate study treatment use or patient harm, while the study drug is in the control of the healthcare professional, or in certain cases, the patient. Such incident may be due to health-care professional practice, product labeling, packaging and preparation, procedures for administration, and systems, including the following: prescribing, order communication, dispensing, nomenclature, compounding, distribution, administration, education, monitoring, and use.

Accidental/Occupational Exposure

Accidental/Occupational Exposure is the unintentional exposure to a study treatment as a result of one's professional or non-professional occupation, or accidental exposure to a nonprofessional to whom exposure was not intended (eg, study drug given to wrong patient).

11.5.2.3 Death

Death is an outcome of an event. All causes of death are SAEs. In the event of death, every effort should be made to obtain a death certificate and if possible, an autopsy report. If the cause of death is unknown, death will be recorded as the event.

11.5.3 Responsibilities of the Investigator

The responsibilities of the Investigator include but are not limited to the following:

- Monitor and record all AEs
- Determine seriousness, severity, and relationship to IP and/or study procedure and/or underlying disease
- Determination of the onset and end date of each event
- Report SAEs to the DSMB, IRB, FDA (Investigator-Initiated IND) and Sarepta within the timelines outlined in Section 11.5.1.
- Report follow-up information on SAEs within the timelines outlined in Section 11.5.
- Ensure source documentation for all AEs are accurate and complete
- Ensure that the study is conducted as defined in this document

11.5.4 Responsibilities of Sarepta

Notification of SUSARs to Sarepta's FDA INDs and NDAs, as applicable, all ex-US regulatory authorities and Investigators in ongoing studies of casimersen, eteplirsen, and golodirsen

12 DATA COLLECTION, QUALITY ASSURANCE, AND MANAGEMENT

12.1 Recording of Data

Clinical data for this study will be captured in an electronic format. Electronic data capture (EDC) will be built by the Nationwide Children's Hospital Research Information. The Investigator, or personnel delegated by the Investigator, will perform primary data collection/perform assessments based on the protocol design and captured in source documentation. All required study information must be recorded on the appropriate CRF screens/forms using the CRF Completion Guidelines for the study. A CRF must be completed for each subject that is enrolled. The study monitor will conduct 100% source data verification to ensure maximum data integrity. All data must be carefully entered in a timely fashion to permit meaningful interpretation and study oversight.

12.2 Quality Assurance

The CRFs will be reviewed at regular intervals by a clinical monitor per the agreed upon Monitoring Plan against the source documentation for identification and clarification of any discrepancies. Automated and manual quality checks will be in place to identify discrepancies, such as missing data, protocol deviations, out-of-range data, other data inconsistencies and compliance. Requests for data clarification or correction will be documented as electronic queries within the CRF and for the Investigator or study coordinator to resolve. All changes to the CRFs will be tracked in an electronic audit trail. Site Study Files will be reviewed for compliance throughout the study.

Audits may be carried out by the IIS Supporter's representatives, and inspections may be performed by IRBs or regulatory authorities before, during, or after the study. The Investigator will allow and assist the IIS Supporter's representatives and any regulatory agency to have direct access to all study records, CRFs, subject medical records and other source documentation, IP dispensing records and IP storage area, study facilities, and any other source documentation.

The Investigator must make study files and data accessible to the study monitor, to other authorized representatives of the IIS Supporter, and to the appropriate regulatory authority inspectors such as the United States Food and Drug Administration (US FDA).

12.3 Retention of Study Documents

At study completion, all CRF data will be copied onto a compact disc (CD) and provided to the Investigator for retention in the Study Files. The supporting Site Study Files must be retained by the Investigator for a period of 3 years after the investigation is discontinued and regulatory authorities are notified.

However, these documents must be retained for a longer period if required by the applicable regulatory requirements or by an agreement with the IIS Supporter. No study documents will be destroyed or moved to a new location without prior written approval from the IIS Supporter. If the Investigator relocates, retires, or withdraws from the clinical study for any reason, all records that are required to be maintained for the study are to be transferred to an agreed-upon designee.

Subject records or other source data must be kept for the maximum period of time mandated by the hospital, institution, or private practice, but not less than 15 years.

If off-site archiving is used, all records must be retrieved and made available for review at the time of an audit or regulatory authority inspection.

12.4 Essential Study Documents

Essential study documents are among the critical documents required before study enrollment is to occur. Essential documents, as well as supplemental information such as the Investigator's Brochure or package insert for each product (as applicable), final protocol, as specified in the Clinical Operations Manual and/or Regulatory Binder, must be kept on-site in a designated study site file.

The study site files will also contain, including but not limited to, subject accountability records, drug accountability (receipt/dispensing) records, Study Sponsor/Investigator correspondence, IRB correspondence, deviations, biological sample records, and SAE and Investigational New Drug (IND) safety reports/Safety Alert Letters/SUSARs.

13 STUDY REPORTS

13.1 Final Study Report

The final study report will include data through the final study visit and the safety follow-up phone call approximately 28 days after the last infusion of study drug.

13.2 Annual Study Report

Within 60 days after the one-year anniversary of the date on which the investigational new drug (IND) application went into effect, and after each subsequent anniversary until the trial is completed, the Principal Investigator will submit information set forth as follows:

(a) Clinical Trial Information. This will be a brief summary of the status of the trial in progress or completed during the previous year. The summary will include the following information for the trial: (1) the title and purpose of the trial; (2) clinical site; (3) the Principal Investigator; (4) clinical protocol identifiers, NCH IRB protocol numbers, and the FDA IND application number; (5) participant population (such as disease indication and general age group); (6) the total number of participants planned for inclusion in the trial; the number entered into the trial to date; the number whose participation in the trial was completed; and the number who dropped out of the trial with a brief description of the reasons; (7) the status of the trial, e.g., open to accrual of subjects, closed but data collection ongoing, or fully completed, and (8) if the trial has been completed, a brief description of any study results.

(b) Progress Report and Data Analysis. Information obtained during the previous year's clinical and non-clinical investigations, including: (1) a narrative or tabular summary showing the most frequent and most serious adverse experiences by body system; (2) a summary of all serious adverse events submitted during the past year; (3) a summary of serious adverse events that were expected or considered to have causes not associated with the use of the gene transfer product such as disease progression or concurrent medications; (4) if any deaths have occurred, the number of participants who died during participation in the investigation and causes of death; and (5) a brief description of any information obtained that is pertinent to an understanding of the gene transfer product's action, including, for example, information about dose-response, information from controlled trials, and information about bioavailability.

(c) A copy of the updated clinical protocol including a technical and non-technical abstract.

13.3 Data and Safety Monitoring Plan

13.3.1 The Data Safety Monitoring Plan

A Data and Safety Monitoring Board (DSMB) will act in an advisory capacity to review participant safety and study progress for the "48-Week, Open Label, Study to Evaluate the Efficacy and Safety of Casimersen, Eteplirsen and Golodirsen in Subjects with Duchenne Muscular Dystrophy carrying eligible DMD duplications " study.

The activities and composition of this committee will be detailed in the DSMB Charter, which will be ratified during the initial DSMB meeting, which will occur prior to the commencement of dosing of the patients.

13.3.1.1 DSMB Membership

The DSMB membership consists of 3-4 persons completely independent of the investigator who have no financial, scientific, or other conflicts of interest with the trial. Current or past collaborators of [name] must note any significant conflict of interest before their eligibility to serve on the DSMB is approved.

The DSMB will include experts in or representatives of the fields of:

- Pediatric Neurology and Neuromuscular Diseases
- Muscular Dystrophy Clinical Care
- Clinical Research and Clinical Trials
- Pulmonology
- Complex Care

Individuals invited to serve on the DSMB as either voting or non-voting members must disclose any potential conflicts of interest, whether real or perceived. Conflicts of interest can include professional, proprietary, and miscellaneous interests as described in the NIH Grant Policy Statement and 45 CFR Part 94. Potential conflicts that develop during a member's tenure on a DSMB must also be disclosed. Written documentation attesting to an absence of conflict of interest is required.

14.1.2 DSMB Responsibilities

Responsibilities of the DSMB are to:

- Review the research protocol, informed consent documents and plans for data and safety monitoring;
- Evaluate the progress of the trial, including periodic assessments of data quality and timelines, participant recruitment, accrual and retention, participant risk versus benefit, trial site performance, and other factors that can affect study outcome;
- Consider factors external to the study when relevant information becomes available, such as scientific or therapeutic developments that may have an impact on participant safety or the ethics of the trials;
- Review study performance, make recommendations and assist in the resolution of problems reported by the Principal Investigator;
- Protect the safety of the study participants;
- Review safety data to determine whether to recommend dose escalation;
- Ensure the confidentiality of the trial data and the results of monitoring; and
- Assist by commenting on any problems with study conduct, enrollment, and sample size and/or data collection.

An additional responsibility of the non-voting Sarepta member is to provide additional or relevant safety information occurring in other Sarepta clinical trials using these three products that is relevant and pertinent to the safety of the participants in this NCH clinical trial.

13.4 Safety Reporting and Meetings

Reports describing the status of the study will be prepared by the Principal Investigator's staff and sent to the DSMB before every meeting, every 6 months beginning with the first infusion, or at the DSMB's request.

A meeting (either by teleconference or webcast) with the DSMB will be scheduled prior to study initiation and reports will be submitted prior to a scheduled meeting for review by the DSMB.

Reports will include the following:

- A brief narrative of the study status, including the target enrollment, current and projected time to completing enrollment. Any significant events and/or difficulties should be briefly described in this narrative.
- A brief narrative for each participant describing gender, age, race and ethnicity and other relevant demographic characteristics. The narrative for each participant should briefly describe his/her study status (i.e., dose level, visit number, adverse event information);
- A timeline outlining the study progress relative to visit number for each participant, as well as time points for each SAE. A total for Adverse Events (AEs) for each participant should be included.
- A summary of AEs by severity levels;
- A listing of AE details grouped by participant;
- A listing of SAE details grouped by participant;
- A summary of TEAEs by System Organ Class, Preferred Term, and Maximum Severity
- A listing of deaths
- A summary of clinically significant laboratory test results

14 STATISTICAL CONSIDERATIONS

Analysis for both efficacy and safety will be occur for each subject.

14.1 General Considerations

This section describes the rules, conventions, statistical analysis, and presentation of data for this study.

All available data will be included in data listings and tabulations. No imputation of values for missing data will be performed. Percentages of subjects with AEs or laboratory abnormalities will be based on non-missing values.

All data collected in this study will be presented using summary tables and subject data listings. Summary statistics for raw and change from Baseline data of continuous variables will minimally include n, mean, standard deviation (SD), minimum, median, and maximum. For categorical variables, frequencies and percentages will be presented. Graphical displays will be provided as appropriate.

Endpoints will be assessed primarily using simple descriptive statistics and/or inferential statistics. Baseline will generally be defined as the last available value before dosing.

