5 STUDY OBJECTIVES

5.1 Primary Objective

Primary objective are to evaluate the effect of either casimersen, eteplirsen, or golodirsen on:

- To evaluate the efficacy of casimersen (previously SRP-4045), eteplirsen (previously AVI-4658), or golodirsen (previously SRP-4053) on dystrophin expression as assessed by quantification of protein in muscle biopsy tissue by western blot.
- Safety and tolerability in a population of subjects with relevant exon duplications using the following outcome measures:
 - Adverse events (AEs), serious adverse events (SAEs), deaths, and discontinuations due to AEs
 - Laboratory testing may include the following (See Section 9 for details):
 - Hematology
 - Coagulation
 - Chemistry
 - Urinalysis
 - Cardiac function including ECG and ECHO
 - Vital signs
 - Physical examination findings

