9 STUDY VISITS

The schedule outlining the study assessments and times of assessments is shown in Section 9.9 and all procedures are described in detail in Section 10. **All assessments scheduled on the same day as study treatment administration are to be completed prior to initiation of study treatment infusion.**

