9.1.2 Screening

The screening evaluations will take place over two visits to allow time for assessment of all available criteria before the subject undergoes sedation.

9.1.2.1 Screening Day 1

The following assessments will occur at this visit:

- Informed Consent
- Assent, if applicable
- Medical history
- Concomitant Medications
- Full Physical Exam
- Vital Signs
- Weight

The following blood lab work will occur at this visit:

- Hepatitis B, C and HIV
- Complete Metabolic Panel (CMP)
- Amylase
- Gamma-glutamyl transpeptidase (GGT)
- Complete Blood Count (CBC)/Differential
- Coagulation Measures
- Uric Acid
- Lactate dehydrogenase (LDH)
- C-reactive Protein (CRP)
- Creatine Kinase (CK)
- Cystatin C
- Genotyping of *DMD*, if not previously done

The following urine lab work will occur at this visit:

- Urinalysis

9.1.2.2 Screening Day 2

The following will be assessed at this visit:

- Adverse Events
- Concomitant Medications
- ECHO
- ECG
- Bayley scale of Infant Development (6 to 36 months of age)
- 100M – ambulant subjects (3.5 years until non-ambulant)
- NSAA (3 years to non-ambulant)
- Active-seated – non ambulant subjects (5 years and older)
- Pulmonary functional test (PFT) (10 years and older)
- Timed functional tests for (ambulant subjects 3 years and older)
- Pediatric Outcomes Data Collection Instruments (PODCI, ages 2-17)
- Patient-Reported Outcomes Measurement Information System (PROMIS) Upper Extremity Report (ages 18+)
- Assessment of inclusion and exclusion criteria
- Height

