9.1.3 Baseline

The baseline visit should occur 3-5 weeks after screening is completed and will occur over two days.

9.1.3.1 Day 1

The following assessments will occur at this visit:

- **Confirmation of eligibility**
- Medical history
- Adverse Events
- Concomitant Medications
- Full Physical Exam
- Vital Signs
- Height
- Weight
- ECG
- Bayley scale of Infant Development (6 to 36 months of age)
- 100M – ambulant subjects (3.5 years until non-ambulant)
- NSAA (3 years to non-ambulant)
- Active-seated – non ambulant subjects (5 years and older)
- Pulmonary functional test (PFT) (10 years and older)
- Timed functional tests for (ambulant subjects 3 years and older)
- Pediatric Outcomes Data Collection Instruments (PODCI, ages 2-17)
- Patient-Reported Outcomes Measurement Information System (PROMIS) Upper Extremity

Report (ages 18+)

The following blood lab work will occur at this visit:

- Complete Metabolic Panel (CMP)
- Amylase
- Gamma-glutamyl transpeptidase (GGT)
- Complete Blood Count (CBC)/Differential
- Coagulation Measures
- Uric Acid
- Lactate dehydrogenase (LDH)
- C-reactive Protein (CRP)
- Creatine Kinase (CK)
- Cystatin C

The following urine lab work will occur at this visit:

- Urinalysis

9.1.3.2 Day 2

A baseline open muscle biopsy will be performed in one gastrocnemius muscle or alternate muscle. (Note that the rationale and methods of muscle biopsy site selection and performance for this and subsequent biopsies are discussed in Section 10.2.1). If in the discretion of the principal investigator, an implanted venous access port needs to be placed prior to infusion, this placement may occur at the same time as the muscle biopsy. RNAseq analysis will be completed on tissue from this muscle biopsy.

If in the opinion of the Principal Investigator, a PORT placement is indicated, all attempts will be made to have this occur during this same sedation event (see Section 8.2 for full details), but if it is not feasible, a separate visit will be scheduled to place the port.

9.2 Week 1

Week 1 should occur within 4 weeks of the Baseline Functional Assessment Visit. If the Week 1 visit is > 4 weeks after Baseline, the subject is required to repeat the Baseline functional assessments to reconfirm eligibility.

Infusion with the study drug will begin at Week 1 and will occur weekly through the week 48 visit. For details regarding the infusion, please see Section 8.2.

The following assessments will occur at this visit:

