- **Confirmation of eligibility**
- Medical history
- Adverse Events
- Concomitant Medications
- Full Physical Exam
- Vital Signs
- Weight

- Infusion

The following blood lab work will occur at this visit:

- Complete Metabolic Panel (CMP)
- Amylase
- Gamma-glutamyl transpeptidase (GGT)
- Complete Blood Count (CBC)/Differential
- Coagulation Measures
- Uric Acid
- Lactate dehydrogenase (LDH)
- C-reactive Protein (CRP)
- Creatine Kinase (CK)
- Cystatin C

The following urine lab work will occur at this visit:

- Urinalysis

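### Does taking the last value before dosing as baseline distort the CK, LDH, AST, ALT and CRP changes, because the Week 1 sample follows the muscle biopsy?

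*Combined protocol and SAP*

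**What the plan says.** Section 14.1 sets one general rule: "Baseline will generally be defined as the last available value before dosing". It names no exception for laboratory data, although *generally* leaves room for one. Section 14.3.2.2 then summarises actual values and change from Baseline for the laboratory parameters, by visit and treatment group.

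The order of events before the first dose comes from four places:

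- Section 9.1.3: "The baseline visit should occur 3-5 weeks after screening is completed and will occur over two days". Section 9.1.3.1 puts the metabolic panel (which contains AST and ALT, per Section 10.1.2), LDH, CRP and CK on Day 1.
- Section 9.1.3.2, Day 2: "A baseline open muscle biopsy will be performed in one gastrocnemius muscle or alternate muscle".
- Section 10.2.4 requires this biopsy before any dose, within four weeks after the Baseline functional visit. It states no minimum interval between biopsy and first dose.
- Section 9.2 repeats the same panel at Week 1. Section 9 places it before the drug: "All assessments scheduled on the same day as study treatment administration are to be completed prior to initiation of study treatment infusion".

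At Week 48, blood is drawn on Day 1 (Section 9.8.1) and the second biopsy follows (Section 9.8.2).

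**The concern.** Cutting into muscle could plausibly release muscle enzymes and raise an inflammatory marker. If one of these analytes were still raised at Week 1, the baseline would be too high and a later rise would look too small, which is the unfavourable direction for a safety summary. One Week 1 draw is the reference for six later laboratory visits (Weeks 4, 8, 12, 24, 36 and 48). The Week 48 sample precedes the second biopsy, so the two ends of the change differ in recent surgery.

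Section 5.1 makes safety a primary objective ("Safety and tolerability in a population of subjects with relevant exon duplications using the following outcome measures"), there are about six subjects, and no control arm would show a shared artefact. A pre-biopsy sample is already collected, so the plan seems to pass over the better reference.

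**Working it through.** The documents give no figure for a biopsy effect, so there is none to reproduce. The check has four steps.

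**1. Which sample the rule selects.** The order is Baseline Day 1 panel, biopsy, Week 1 panel, first infusion. The last value before dosing is therefore the Week 1 value. This part of the concern is correct.

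**2. Time from biopsy to Week 1.** Inputs: screening begins about 8 weeks before Week 1, taken as day 56 (Section 9.1); Baseline falls 3 to 5 weeks after screening is completed (Section 9.1.3); first dose within 28 days of the Baseline functional visit (Section 10.2.4); biopsy on Day 2. Let *d* be the days between the two screening visits, which the documents do not give. Baseline Day 1 falls on day *d*+21 to *d*+35. The gap from biopsy to Week 1 is then (21-*d*) to (35-*d*) days, capped at 28, less 1.

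| *d* (assumed) | Biopsy to Week 1 |
|---|---|
| 0 | 20 to 27 days |
| 7 | 13 to 27 days |
| 14 | 6 to 20 days |

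A shorter gap is permitted because no minimum is stated, but nothing in the schedule plans for one.

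**3. What a residual elevation would do.** If the Week 1 value is (1+*x*) times the pre-biopsy value and nothing else changes, the apparent later change is 1/(1+*x*) - 1. Every *x* is an assumption.

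| *x* | Unchanged analyte appears as | Mean of a two-subject group, one affected |
|---|---|---|
| 0% | 0% | 0 points |
| 5% | -4.8% | -2.4 points |
| 10% | -9.1% | -4.5 points |
| 25% | -20.0% | -10.0 points |
| 50% | -33.3% | -16.7 points |

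The last column halves the one before it; the split of subjects over the three drugs is not given. Sections 14.1 and 14.3.2.2 plan changes, not percent changes, so these figures only illustrate scale. In units, the shift is -*x* times the pre-biopsy value.

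**4. What the pre-biopsy reference would do.** Suppose an elevation *y* remains at Week 4. Change from Week 1 is (1+*y*)/(1+*x*) - 1; change from Baseline Day 1 is +*y*. With *x* = 25% and *y* = 10%, these are 1.10/1.25 - 1 = -12.0% and +10.0%. The error changes sign and now looks like a rise on drug.

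Week 4 is nominally 21 days after Week 1 and may be taken a week either side, so 14 to 28 days after it. With a 6-day gap it can fall 6 + 14 = 20 days after surgery. At the planned gap it falls 20 + 14 = 34 to 27 + 28 = 55 days after. The reversed error therefore arises mainly when the gap is short, which is also when a raised Week 1 baseline would carry weight.

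**The case for a change.** The strongest reply is that the remedy costs almost nothing. The pre-biopsy sample exists, a second change column would show whether the biopsy mattered, and nobody need assume an effect to add it. If an effect exists and fades quickly, a pre-biopsy reference would be wrong at Week 4 at most, whereas a raised Week 1 value would carry into all six later visits. Section 10.2.4 does permit a gap much shorter than planned, and a separately scheduled port placement (Section 9.1.3.2) could be another procedure before Week 1.

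The sample order and the arithmetic stand. What does not stand is the step to a defect. The mechanism, its direction and the choice of these five analytes over the rest of the panel all come from outside the documents, and the range of assumed effects includes zero. The proposed reference would also give AST and ALT a different baseline from the rest of the same metabolic panel.

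The extra column adds little. Section 14.3.2.2 already summarises actual values by visit, and Sections 14.1 and 14.3.2 put all safety data in listings. With about six subjects, Baseline Day 1 and Week 1 can be compared subject by subject. The tables of abnormal laboratory changes in Section 14.3.2.2 do not name their parameters, so no effect on them can be shown.

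A related point concerns functional tests. Section 9.2 says: "If the Week 1 visit is > 4 weeks after Baseline, the subject is required to repeat the Baseline functional assessments to reconfirm eligibility". Such a repeat might follow the biopsy and become the functional baseline. It arises only if Week 1 is more than four weeks after Baseline, which Section 10.2.4 rules out unless the repeat restarts that window. It would touch only exploratory measures, whose summaries are optional under Section 14.3.1.3. The wording of Sections 9.2 and 10.2.4 on this window must be reconciled, but that has no bearing on the laboratory baseline.

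**Conclusion.** The concern does not hold. Section 14.1 does select a post-biopsy sample for these five analytes, but the last value before dosing is a standard and defensible baseline: it is closest to the first infusion and already reflects whatever happened before treatment. Choosing the pre-biopsy value instead would be a trade-off on which statisticians can reasonably differ.

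The possible shift runs from 0 to -33.3% for an affected subject under assumed elevations of 0 to 50%. It is probably small at the planned 20 to 27 days. That interval assumes Week 1 on day 56, both screening visits on one date and the biopsy on Day 2; it shortens to 6 to 20 days if the screening visits are 14 days apart.

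Section 14.3.2 makes the safety analysis descriptive. No hypothesis test and no dystrophin endpoint depends on the laboratory baseline, and a reader of the listings can see both pre-dose values. The conclusion would need another look only if the sponsor had data showing a lasting biopsy effect on these analytes, or if biopsies were in practice done within a few days of the first dose.
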